## 5.7 Other Analyses

Other analyses may be conducted as appropriate.

## 5.8 Exploratory Analyses

Exploratory analyses may be conducted as appropriate. More details will be given in a separate analysis plan if necessary.

# 6 INTERIM ANALYSES

There will be interim analyses to define the MTDs and/or RP2Ds prior to initiating the Expansion phase of the study. Other interim analyses may be performed to determine if a different dosing schedule (eg, BID) or frequency (eg, 2-weeks on/1-week off) may be preferable. Database locks are not required to perform these analyses. Safety and PK summaries may be provided periodically.

# 7 CHANGES IN THE PLANNED ANALYSES

SAP Amendment 0.1: DLT analysis set is defined for the evaluation of DLTs.

SAP amendment 0.2: Efficacy summaries will only include HCC subjects. Efficacy listings will include both HCC and ICC subjects who were enrolled prior to Protocol Amendment 8.

# 8 DEFINITIONS AND CONVENTIONS FOR DATA HANDLING

The Baseline value will be defined as the last non-missing measurement prior to the first dose of the study drug. A Baseline value doesn't have to be collected in the Baseline period.

Descriptive statistics for continuous variables will be reported using number of non-missing measurements (n), mean, standard deviation (SD), median, the first quartile (Q1), the third quartile (Q3), minimum and maximum.

Descriptive statistics for categorical variables will be summarized as number (percentage) of subjects.

P-values will be presented with 3 decimal places or “< .001”, rates will be presented with 1 decimal place or 0, CIs of rates will be reported as two-sided and calculated using Clopper-Pearson method, and time-to-event variables will be estimated using Kaplan-Meier method.

Further definitions and conventions for data handling will be presented in “Programming Specifications”.

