9.5.1.4.6 ELECTROCARDIOGRAMS AND HOLTER MONITORING

For all subjects, 12-lead ECGs will be obtained as designated in the Schedule of Procedures/Assessments ([Table 6](#) and [Table 7](#)). In the event of any alteration, or if clinically necessary, an echocardiogram and/or cardiac enzymes should be performed.

In Part 1, Dose Escalation, the effects of H3B-6527 on cardiovascular repolarization will be evaluated via 12-lead continuous Holter/ECG monitoring on C1 Day 1 and on Day 8. The continuous Holter monitoring must begin at least 1 hour prior to dose on C1 Days 1 and 8 and will continue through 10 hours postdose for all subjects regardless of dose schedule (QD or BID) in the Dose Escalation Phase of the study.

Additionally, Holter monitoring/ECGs (12-lead) are to be collected 1 hour before the first dose (at 3 time points) and at 0.5, 1, 2, 4, 6, 8, and 10 hours postdose on C1 Days 1 and 8. At each of these time points, subjects should be supinely resting for at least 10 minutes before

and 5 minutes after the nominal time. When coinciding, blood collection, vital signs, and 12-lead safety ECGs should be performed immediately after the time window for ECG extraction.

Screening & baseline ECGs will be performed as singles. However, if clinically indicated, triplicates will be performed at screening and baseline. All other ECGs after screening/baseline will be performed as singles.

Individual ECGs will be extracted from the Holter recordings at specified time points per ECG manual and will be evaluated by a central laboratory. QT intervals will be measured from Lead II and will be corrected for QTcF correction factors. The primary QTc parameter will be QTcF. Secondary parameters (QT corrected for heart rate using Bazett's formula [QTcB], QT, QRS, PR, and heart rate) and wave forms (T waves) will be evaluated.

An ECG abnormality may meet the criteria of an AE as described in this protocol (see [Section 9.5.1.4.1](#)) and the CRF Completion Guidelines. In these instances, the AE corresponding to the ECG abnormality will be recorded on the Adverse Events CRF.

For ECG abnormalities meeting the criteria of an SAE (see [Section 9.5.1.4.2](#)), the site must fax or email the SAE report including the ECG report to the Sponsor using the SAE form (see [Section 9.5.4.1](#)).

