f: Ophthalmic examination by an ophthalmologist will be performed at Screening (or within 7 days prior to Day 1 of each applicable cycle), on C1 Day 8, C2 Day 1, and on Day 1 of all subsequent cycles (through C6), and at the off-treatment visit. Ophthalmic examinations performed within 8 weeks of C1 Day 1 can be used in the event of a rescreen. After C6, OCT will be required only on Day 1 of every other cycle. As part of the ophthalmological examination, a visual acuity test, funduscopic examination (mydriatic test if necessary), slit-lamp examination (fluorescein staining will be performed if necessary), and an anterior eye OCT for assessing the central corneal thickness will be performed. The central corneal thickness will be measured as part of the anterior eye OCT and recorded on the CRF.

g: MUGA scans or echocardiograms will be performed during the Pretreatment Phase, during the OTV (window of ± 1 week), and if clinically indicated during treatment. MUGA scans or echocardiograms performed within 8 weeks of C1 Day 1 can be used in the event of a rescreen. MUGA scans and echocardiograms will be performed locally in accordance with the Institution's standard practice.

h: A serum pregnancy test (β -hCG) will be performed during Screening for all premenopausal women and postmenopausal women who have been amenorrheic for less than 12 months. A urine or serum pregnancy test will be performed before the first H3B-6527 dose and at the OTV.

i: Vital signs include BP, HR, RR, and body temperature, as well as weight. BP, HR, and RR will be collected after the subject has been sitting for 5 minutes. Height will be measured during Screening only.

j: Screening and baseline ECGs will be performed as singles. However, if clinically indicated, triplicates will be performed at screening and baseline. All other ECGs after screening/baseline will be performed as singles.

k: Continuous Holter monitoring will begin at least 1 hour prior to dosing through 10 hours post-dose on C1 Days 1 and 8. Subjects should be supinely resting for at least 10 minutes prior to and 5 minutes after the following time points, pre-dose (3 time points within 1 hour of dose) and 0.5, 1, 2, 4, 6, 8 and 10 hours postdose. When coinciding, blood draws, vital signs and 12-lead safety ECGs should be performed immediately after the time window for ECG extraction.

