## 5.6 Safety Analyses

All safety analyses will be performed on the Safety Analysis Set and “as treated” basis except the evaluation of DLT and determination of the MTD. The number (percentage) of DLT will be summarized on and the determination of the MTD will be based on DLT Analysis Set in the Dose Escalation part.

Subjects who do not receive study drug for at least 17 of 21 days (80%; not necessarily consecutively) during the first cycle for reasons not considered to be a DLT by both the investigators and the Sponsor will be replaced. The subjects who are replaced will not be considered evaluable for DLT assessments.

Safety data include all AEs, SAEs, clinical laboratory tests, vital signs, ECGs, MUGA/echocardiogram, and ophthalmic examinations.

Safety parameters will be summarized using descriptive statistics (mean, standard deviation, median, Q1, Q3, and range for continuous variables; numbers and percentages for categorical measures).

The effects of H3B-6527 on cardiovascular repolarization will be evaluated via 12-lead continuous cardiac Holter monitoring around first dose administration on C1 Day 1 and Day 8 in the dose escalation part of the study only. Individual ECGs will be extracted from the Holter recordings at specified time points per ECG manual and will be evaluated by a central laboratory. QT intervals will be measured from Lead II and will be corrected for heart rate (QTc) using Fredericia’s (QTcF) correction factors. The primary QTc parameter will be QTcF; secondary parameters (QTc corrected using Bazett’s formula [QTcB], QT, QRS, PR, and heart rate) and wave forms (T waves) will be evaluated.

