#### 5.6.5 Electrocardiograms

Descriptive statistics for ECG parameters (i.e. QTcF, QTcB, QT, QRS, heart rate and waveforms) and changes from baseline will be summarized over time. Shift tables will present changes from baseline in ECG interpretation (categorized as normal; abnormal, not clinically significant; and abnormal, clinically significant) to end of treatment.

In addition, the number (percentage) of subjects with at least 1 post baseline abnormal ECG result in QTcF during the treatment period will be summarized. Clinically abnormal ECG results in QTcF will be categorized as follows:

Absolute QTc interval prolongation:

- QTc interval > 450 ms
- QTc interval > 480 ms
- QTc interval > 500 ms

Change from baseline in QTc interval:

- QTc interval increases from baseline > 30 ms
- QTc interval increases from baseline > 60 ms

Listings of ECG results, ECG abnormalities and Holter recordings will be provided.

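### The SAP's last-value baseline rule would use at most one of the three pre-dose Holter QTcF readings in Part 1, and the ECG source for the QTcF change summaries is not named

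*SAP*

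**What the plan says.** **Baseline.** SAP 8 contains the only baseline definition: "The Baseline value will be defined as the last non-missing measurement prior to the first dose of the study drug". It adds that the value need not come from the Baseline period, so pre-dose readings on Cycle 1 Day 1 qualify. The same section closes with "Further definitions and conventions for data handling will be presented in" a separate programming document, which is not part of the public material.

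**Holter readings.** Protocol 9.5.1.4.6 has Holter ECGs "collected 1 hour before the first dose (at 3 time points) and at 0.5, 1, 2, 4, 6, 8, and 10 hours postdose" on Cycle 1 Days 1 and 8. Table 6, footnote k, repeats the three pre-dose points. SAP 5.6 limits this evaluation to "C1 Day 1 and Day 8 in the dose escalation part of the study only", has a central laboratory read the extracted ECGs, and states "The primary QTc parameter will be QTcF". Neither document says how the three pre-dose readings are to be combined.

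**Safety ECGs.** Both parts also have scheduled 12-lead safety ECGs. For these, "Screening & baseline ECGs will be performed as singles", with triplicates only if clinically indicated.

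**Use of the change.** SAP 5.6.5 summarises ECG parameters and their changes from baseline. It counts subjects with at least one abnormal post-baseline QTcF result, including "QTc interval increases from baseline > 30 ms" and the corresponding >60 ms category. It does not name the ECG source for these tables, and it mentions Holter recordings only as a listing.

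**The concern.** A baseline reading enters every change computed from it. If one pre-dose reading happens to be low, all of that subject's post-dose changes are pushed up together, and a count of subjects with any change above 30 ms picks this up. The trial already collects three readings close together before the first dose. A rule that keeps one of them gives up precision that costs nothing to obtain.

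The rule may also select a reading of a different kind. Table 6 schedules a safety 12-lead ECG on Cycle 1 Day 1. Footnote k places coinciding safety ECGs directly after the Holter extraction window, and footnote y holds the dose back on visit days until evaluations are done. The last ECG before the first dose could therefore be a single safety ECG, which would then be set against centrally read Holter values.

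Change in ECG parameters is part of the primary safety endpoint (SAP 5.1.1). Part 1 tables are broken down by dose cohort (SAP 5), with cohorts of 3 to 6 subjects, so one or two chance flags can alter the look of a cohort.

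**Working it through.** The plan states no QTc variability or precision target, so there is no figure of its own to reproduce. The SDs below are assumptions, shown over a range.

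**Inputs from the documents**
- Pre-dose Holter points on Day 1: 3.
- Post-dose Holter points: 7 on each of Days 1 and 8, so 14.
- Part 1 size: 30 to 48 subjects.
- Thresholds: >30 ms and >60 ms.

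**Assumed**
- Sr, the SD of one reading within a session: 6 to 15 ms.
- So, an error shared by all readings in one session: 0, 5 or 8 ms.
- Normal errors and no drug effect.

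**Step 1: SD of one change.** For readings in different sessions (Day 8 against Day 1):
- single baseline: variance = 2So² + 2Sr²
- mean of three: variance = 2So² + Sr²(1 + 1/3)

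With So = 0 the ratio of SDs is √((4/3)/2) = 0.816, a fall of 18.4%. At Sr = 10 ms, the SD goes from √200 = 14.14 ms to √133.3 = 11.55 ms. With So = 5 ms the ratio is 0.90 to 0.84 over Sr = 6 to 15 ms. With So = 8 ms it is 0.94 to 0.86. The fall is therefore 6-16% when a session error is present. For post-dose readings on Day 1 itself the shared error cancels under this model, and the 18% applies.

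**Step 2: chance of >30 ms at one time point.** At Sr = 10 ms and So = 0: 30/14.14 = 2.12, an upper tail of 1.69%; and 30/11.55 = 2.60, a tail of 0.47%.

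**Step 3: chance of >30 ms at any of 14 post-dose points.** Simulation of 400,000 subjects, taking the largest post-dose value minus either the last pre-dose reading or the mean of three:

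| Sr (ms) | So (ms) | Last value | Mean of 3 | Expected flags in 48 |
|---|---|---|---|---|
| 6 | 0 | 0.24% | 0.01% | 0.1 vs <0.1 |
| 8 | 0 | 3.9% | 0.8% | 1.9 vs 0.4 |
| 10 | 0 | 12.8% | 5.6% | 6.1 vs 2.7 |
| 10 | 5 | 16.1% | 9.4% | 7.7 vs 4.5 |
| 12 | 0 | 24.2% | 16.0% | 11.6 vs 7.7 |
| 15 | 0 | 39.4% | 34.7% | 18.9 vs 16.6 |

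With 30 subjects, Sr = 10 ms and So = 0, the expected flags are 3.8 versus 1.7.

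**Step 4: one cohort of six.** At Sr = 10 ms and So = 0, the expected number of flags is 6 × 0.128 = 0.77 versus 6 × 0.056 = 0.34. The chance of at least one is 1 − (1 − 0.128)⁶ = 56% versus 1 − (1 − 0.056)⁶ = 29%.

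**Step 5: the >60 ms category.** With So = 0, the chance over 14 points is at most 0.25% for Sr up to 12 ms under either baseline, and 2.4% versus 0.4% at 15 ms. The effect is essentially confined to >30 ms.

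**The case against.** The strongest case against runs as follows.

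- **The rule is generic.** SAP 8 names neither QTcF nor Holter. A reader might infer that the plan has decided to discard two of the three readings. It has not said so; that is only what the rule gives when applied literally. This stands and limits the claim.
- **The outlier table may not use Holter data.** The matching text in Protocol 9.7.1.8.5 opens with all subjects and refers to the whole treatment period, whereas Holter covers two days of Part 1. If the table uses safety ECGs, a single baseline is by design and the 14-point calculation describes other data. This also stands as an ambiguity. Against it, SAP 5.6 makes QTcF the primary QTc parameter in its Holter paragraph, and the protocol section carrying these categories is titled for both ECGs and Holter monitoring. The source has to be stated either way.
- **Programming specifications may settle it.** SAP 8 and 9 defer derivation rules. But SAP 8 already defines baseline, and SAP 5 requires analyses to follow the SAP, with deviations reported in the study report. A specification that averaged readings would depart from SAP 8 as written.
- **The size is assumed.** This stands in full. At 6 ms the effect is negligible, at 15 ms it is small in relative terms, and session error shrinks it.
- **Little turns on it.** No test or escalation rule uses the >30 ms count, and the DLT table has no criterion expressed as a change in QTc. The QTc adverse-event rule in Protocol 9.5.1.4.1 requires QTcF above 450 ms together with a rise above 60 ms. The absolute categories do not involve baseline. A single reading is noisier, not biased.

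**Conclusion.** The point holds as a precision gain in a descriptive Part 1 safety summary, together with a missing statement of ECG source. Read literally, SAP 8 uses one pre-dose value where three Holter readings exist. Averaging them lowers the SD of change by about 18% with independent readings, and by about 6-16% for Day 8 changes under an assumed session SD of 5-8 ms. The effect on >30 ms flags ranges from negligible at a reading SD of 6 ms to roughly a halving at 10 ms with independent errors, and is small again in relative terms at 15 ms. All of this rests on assumed SDs, normal errors, no drug effect, and Holter data feeding the table.

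Three stronger readings are not supported. One is that the plan will mislead dose selection: no decision rule uses the count, although safety in general informs the RP2D. Another is that the >60 ms category is materially affected: it is not at reading SDs up to 12 ms. The third is that the remedy extends to Part 2, which has no Holter monitoring.

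**What to change.** - In SAP 5.6.5, name the ECG source for each QTcF summary, including the >30 and >60 ms table: central Holter extraction or safety 12-lead.
- In SAP 8, define the Part 1 Holter baseline as the mean of the available centrally read pre-dose extractions on Cycle 1 Day 1, and use it only for Holter post-dose values.
- Keep the last-value rule for safety ECGs in both parts, so that each change compares readings from one source.

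The cost is a few SAP sentences and one derivation, with no new data. There is a small downside: Holter changes in Part 1 will be more precise than safety-ECG changes in either part, so their category rates are not comparable and should be reported in separate tables.

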# 9 PROGRAMMING SPECIFICATIONS

The rules for programming derivations and dataset specifications are provided in separate documents.

## **10 STATISTICAL SOFTWARE**

All statistical analyses will be performed using SAS 9.4, or later.

## **11 MOCK TABLES, LISTINGS AND GRAPHS**

The shells of TLGs in the study report will be provided in a separate document which will show the content and format of TLGs in detail. Additionally, the Global Study Report Template gives the standard numbering structure for Section 14 tables, figures, and for Appendix 16.2 listings.

